Appendix:

Modified Yale Perioperative Anxiety Scale (14)

Calculation of score: Highest score of the observed behaviour is the score of each category. A partial weighted score is calculated by dividing the score by the total items of that category. All categories used are added together, multiply by 100 and divided by the number of categories used.

Activity

 1. Looking around, curious, playing with toys, reading (or other age-appropriate behavior); moves around holding area/treatment room to get toys or to go to parent; may move toward operating room equipment 2. Not exploring or playing, may look down, fidget with hands, or suck thumb (blanket); may sit close to parent while waiting, or play has a definite manic quality 3. Moving from toy to parent in unfocused manner, non-activity-derived movements; frenetic/frenzied movement or play; squirming, moving on table; may push mask away or cling to parent 4. Actively trying to get away, pushes with feet and arms, may move whole body; in waiting room, running around unfocused, not looking at toys, will not separate from parent, desperate clinging
Vocalizations

 1. Reading (nonvocalizing appropriate to activity), asking questions, making comments, babbling, laughing, readily answers questions but may be generally quiet; child too young to talk in social situations or too engrossed in play to respond 2. Responding to adults but whispers, "baby talk," only head nodding 3. Quiet, no sounds or responses to adults 4. Whimpering, moaning, groaning, silently crying 5. Crying or may be screaming "no" 6. Crying, screaming loudly, sustained (audible through mask)
Emotional expressivity

 1. Manifestly happy, smiling, or concentrating on play 2. Neutral, no visible expression on face 3. Worried (sad) to frightened, sad, worried, or tearful eyes 4. Distressed, crying, extreme upset, may have wide eyes
State of apparent arousal

 1. Alert, looks around occasionally, notices or watches what anesthesiologist does (could be relaxed) 2. Withdrawn, sitting still and quiet, may be sucking on thumb or have face turned into adult 3. Vigilant, looking quickly all around, may startle to sounds, eyes wide, body tense 4. Panicked whimpering, may be crying or pushing others away, turns away
Use of parents

1. Busy playing, sitting idle, or engaged in age-appropriate behavior and doesn't need parent; may interact with parent if parent initiates the interaction
2. Reaches out to parent (approaches parent and speaks to otherwise silent parent), seeks and accepts comfort, may lean against parent
3. Looks to parent quietly, apparently watches actions, doesn't seek contact or comfort, accepts it if offered or clings to parent
4. Keeps parent at distance or may actively withdraw from parent, may push parent away or desperately clinging to parent and not let parent go

Induction Compliance Checklist (16)

Checklist	Score (1 for each category)
Crying, tears in eyes	
Turns head away from mask	
Verbal refusal, says "no"	
Verbalization indicating fear or worry, "where's mommy?" or "will it hurt?"	
Pushes mask away with hands, pushes nurse/ anaesthetist with hands / feet	
Covers mouth/ nose with hands / arms or buries face	
Hysterical crying, may scream	
Kicks / flails legs / arms, arches back, and/or general struggling	
Requires physical restraint	
Complete passivity, either rigid or limp	

Procedure Behaviour Rating Scale (PBRS)

	Description	Score
Cry	Tears in eyes or running down face	
Cling	Physically holds on to parent, significant other, or nurse	
Fear verbal	Says "I'm scared", "I'm afraid" etc	
Pain verbal	Says "Ow", "Ouch," "It hurts," "You're hurting me," etc.	
Groan	Nonverbal, vocal expression of pain or discomfort	
Scream	No tears, raises voice, verbal or nonverbal	
Laugh	Smiling with a chuckling sound	
Stall	Verbal expression of delay ("Wait a minute," "I'm not ready yet", etc or behavioural delay (ignores nurse's instructions)	
Stoic silence	Child does not respond to questions or remarks of others, may appear "trancelike"	
Carry	Has to be physically carried into or out of room or placed on table, not because of physical inability to do so on his or her own	
Flail	Random gross movements of arms or legs, without intention to make aggressive contact	
Nausea verbal	Says "I'm sick," "I feel nauseous," "My stomach feels like I'm going to throw up"	
Vomit	Includes retching, dry heaves	
Urinate/defecate	Soils or wets self	
Kick	Intentional movement of leg(s) to make aggressive physical contact	
Hit	Intentional movement of arm(s) or hand(s) to make aggressive physical contact	

Bite	Intentional closing of jaw to make aggressive physical contact	
Verbal hostility	Says "I hate you," "You're mean," etc.	
Refusal position	Does not follow instructions with regard to body placement on treatment table	
Restrain	Has to be held down because of lack of cooperativeness	
Curse	Verbally utters profanity	
Muscular rigidity	Any of following behaviors: clenched fists, white knuckles, gritted teeth, clenched jaw, wrinkled brow, eyes clenched shut, contracted limbs, body stiffness	
Questions	Nondelay, information-seeking verbal behavior ("What are you doing now?" Is it over yet? etc.)	
Emotional support	Verbal or nonverbal solicitation of hugs, physical comfort, or expression of empathy from parent, significant other, or nurse	
Requests termination	Verbally asks/pleads that procedure be stopped	
Total Score (25):		

- State Trait Anxiety Inventory for Adults
- Read each statement and select the appropriate response to indicate how you feel right now, that is, at this very moment. There are no right or wrong answers. Do not spend too much time on any one statement but give the answer which seems to describe your present feelings best.

State Anxiety Scale Items	0 Not at all	1 A little	2 Somewhat	3 Very much so
1. I feel calm				
2. I feel secure				
3. I am tense				
4. I feel strained				
5. I feel at ease				
6. I feel upset				
7. I am presently worrying over possible misfortunes				
8. I feel satisfied				
9. I feel frightened				
10. I feel comfortable				
11. I feel self-confident				
12. I feel nervous				
13. I am jittery				
14. I feel indecisive				
15. I am relaxed				
16. I feel content				
17. I am worried				
18. I feel confused				
19. I feel steady				
20. I feel pleasant				
Trait Anxiety Scale Items	0 Almost never	1 Sometimes	2 Often	3 Almost always

21. I feel pleasant				
22. I feel nervous and restless				
23. I feel satisfied with myself				
24. I wish I could be as happy as others seem to be				
25. I feel like a failure				
26. I feel rested				
27. I am 'calm, cool, and collected'				
28. I feel that difficulties are piling up so that I cannot overcome them				
29. I worry too much over something that really doesn't matter				
30. I am happy				
31. I have disturbing thoughts				
32. I lack self confidence				
33. I feel insecure				
34. I make decisions easily				
35. I feel inadequate				
36. I am content				
37. Some unimportant thought runs through my mind and bothers me				
38. I take disappointments so keenly that I can't put them out of my mind				
39. I am a steady person				

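### Does the PBRS total need a special rule because it lists laughing among distress behaviours?

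*Combined protocol and SAP*

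**What the plan says.** The section on outcomes and measurements names the PBRS as a secondary outcome. The statistical section compares it between arms with the Mann-Whitney U test. The design section has it rated together with the mYPAS at T1, on the operating table just before induction.

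The form is in the Appendix under "Procedure Behaviour Rating Scale (PBRS". It lists 25 behaviours with a blank score column and ends with "Total Score (25" as the printed maximum. The seventh row is Laugh, described as "Smiling with a chuckling sound". Nothing on the form gives the points per item, the direction of the total, or any reversal.

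The mYPAS in the same Appendix has as level 1 of Emotional expressivity "Manifestly happy, smiling, or concentrating on play", and level 1 of Vocalizations includes "asking questions, making comments, babbling, laughing, readily answers questions but may be generally quiet".

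The headings of the other two observer scales carry a reference number: "Modified Yale Perioperative Anxiety Scale (14" and "Induction Compliance Checklist (16". The PBRS heading carries none.

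**The concern.** Twenty-five rows and a maximum of 25 suggest one point per row, Laugh included. Nearly all the other rows describe distress or resistance, so a higher total reads as worse. On that reading a child who laughs and does nothing else listed scores worse than a child who shows no listed behaviour. The mYPAS, rated at the same moment, ranks the same two children the other way round.

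The intervention is meant to be enjoyable, so more laughing in the virtual reality arm is plausible. Each extra laughing child in that arm would then add a point against the intervention and offset part of a real reduction in distress. Part of the reason given for recruiting 96 pairs is power for secondary outcomes, so a scoring rule that wastes some of it deserves a look. With no rule stated, the handling of Laugh could also be chosen after the results are known.

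**Working it through.** **1. The printed maximum.** Counting the rows of the form gives 25 distinct behaviours, which matches the printed total. Three treatments of Laugh are possible:

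- counted as one point like the rest: maximum 25; a child who only laughs scores 1, a child with no listed behaviour scores 0;
- reverse-scored: maximum 25; the same two children score 0 and 1;
- recorded but not summed: maximum 24, which does not match.

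The printed total therefore rules out only the third. It does not show that Laugh is added in the distress direction.

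**2. The mYPAS direction.** The Appendix rule divides each category score by its number of levels, sums, multiplies by 100 and divides by the number of categories. Level 1 throughout gives (1/4 + 1/6 + 1/4 + 1/4 + 1/4) × 100/5 = 23.3, the minimum stated in the outcomes section, so level 1 is the calm end. Moving Emotional expressivity from level 1 to level 2 (neutral face) adds (1/4) × 100/5 = 5.0, giving 28.3. The laughing, smiling child scores 23.3 on the mYPAS and, if Laugh counts, 1 on the PBRS. The neutral child scores 28.3 and 0. Under that reading the two scales do disagree.

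**3. Effect on the mean difference.** With Laugh counted, the mean 25-item total equals the mean 24-item total plus the proportion who laugh. The offset is therefore the Laugh proportion under virtual reality minus that in controls: 0 if equal, 0.05 points for a rise of 5 percentage points, 0.20 for a rise of 20. The documents give no Laugh rate.

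**4. Illustrative power.** Planned completers are 96 × (1 − 0.375) = 60, or 30 per arm. Everything else here is assumed: Poisson counts of the other behaviours with means 1.0 (control) and 0.5 (virtual reality), Questions shown by 30% in both arms, and a two-sided Mann-Whitney test at 0.05 counting only results that favour virtual reality. The 24-item total without Laugh gives about 45%. The 25-item total gives:

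| Laugh, control → virtual reality | Laugh independent of distress | Laugh only in undistressed children |
|---|---|---|
| 2% → 4% | 40% | 42% |
| 10% → 10% | 42% | 49% |
| 10% → 15% | 34% | 40% |
| 10% → 20% | 28% | 31% |
| 10% → 30% | 16% | 18% |

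If laughing is partly nervous and falls from 15% to 10% with virtual reality, the 25-item total gives about 49% with Laugh independent of distress, a small gain. A repeat simulation agreed with these figures to within about one percentage point.

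**5. The neighbouring item.** Questions raises a similar conflict, because asking questions is also mYPAS level 1. Yet the induction checklist scores a child who asks whether it will hurt under "Verbalization indicating fear or worry". In the same model, Questions at 30% in both arms lowers the power of the 24-item total from about 58% to about 46%. That is more than Laugh costs at equal rates.

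**The case for a change.** The best case for a change is that the gap is real and cheap to close. The checklist printed just above the PBRS states its item score and the mYPAS states a full formula, while the PBRS states nothing and cites no source. Two scales rated together may rank a cheerful child in opposite directions. Two or three sentences would settle it: take the source's rule if there is one, and otherwise draw the PBRS conclusion from a 24-item total without Laugh, with the 25-item total shown beside it.

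The description of the form stands, and so does the point that the scoring should be settled before unblinding. The 24-item total is where the case weakens. It would alter a named instrument and make the result harder to compare with other uses of the scale. It would drop Laugh but keep Questions, which has a similar though more ambiguous conflict with the mYPAS, so the choice of items becomes a matter of taste. Two different instruments need not code one behaviour alike, and laughing on the operating table may be nervous as well as cheerful. A material loss of power appears only when Laugh is assumed to rise clearly with virtual reality, and nothing in the documents supports any particular rise.

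**Conclusion.** No change to the plan follows. The form leaves out its item score, direction and source. That is missing detail on a named instrument, and an analyst would ordinarily fill it by following the scale's own scoring rule, fixed before the allocation is revealed. Replacing the instrument's total with one that omits Laugh is a debatable trade-off with no demonstrated gain.

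The stakes are small: at most 1 of 25 points per child, on one of several secondary outcomes. With equal Laugh rates of 10%, power moves from about 45% to 42% or 49%, depending on which children laugh. It falls to between 16% and 18% only if Laugh is assumed to triple from 10% to 30%, and it rises slightly if Laugh falls with virtual reality.

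This rests on three things the documents do not settle: one point per item with higher meaning worse (inferred from the row count and the content of the other items), the source's treatment of Laugh, and the Laugh rates themselves. The primary mYPAS comparison and the sample size do not depend on any of them.
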